#### **Concomitant Medications**

- Other medication use will be assessed per exclusion criteria. If the participant is to take/start a new medication while in the study they will be asked to inform the study PI immediately to assess concomitant medication use.

#### **Diet and Other Considerations**

There are no dietary or food restrictions

#### **Duration of Therapy**

For Obese patients, Liraglutide will be administered daily for 12-16 weeks. If any of the following occur, the medication will be stopped:

- Pancreatitis (severe abdominal pain, increased amylase/lipase)
- Severe dehydration
- The participant chooses not to continue in the study

Lean controls will not be given study drug.

### **OTHER STUDY PROCEDURES**

#### **Oral Glucose Tolerance Test (OGTT) and Anthropometric Measures**

After consent is obtained and at baseline prior to any study procedures, Anthropometric measures will be taken including weight, percent fat mass, and total fat mass (measured with a Tanita Body Fat Analyzer) and height (measured with a stadiometer). BMI will be calculated (weight [kg] /height [m^2]). A urine pregnancy test will be performed on females.

Lean young adults will complete 1 OGTT (at baseline) and each obese young adult will complete 2 OGTTs (one at baseline and one at week 10 of the intervention with liraglutide).

Subjects will receive 75g glucose drink orally (Glucola). An intravenous (IV) catheter will be placed and blood samples will be taken for glucose and insulin assays at time points -20, 0, 10, 20, 30, 45, 60, 75, 90, 105, 120 minutes. In addition, fasting acyl-ghrelin, leptin, HgbA1c, GLP-1 will be drawn. Whole body insulin sensitivity index (WBISI) will be calculated (WBISI=10,000/[□(FPG x fasting plasma insulin) x (mean OGTT glucose concentration x mean OGTT insulin concentration)]) as a measure of insulin resistance. No more than 50 ml of blood will be drawn on the OGTT day.

## Continuous Glucose Monitor (CGM)

CGM enables measurement of glucose levels continuously throughout the day. To assess glucose variability, participants will be asked to use the CGM (FreeStyle Libre Pro) for up to 14 days. During their screening/baseline visit, a CGM sensor/transmitter will be placed on the participant's upper arm and attached with an adhesive patch by a trained study staff member. The sensor includes a wire-like tip which will be under the participant's skin in their fat tissue. The participants will be taught how to use the CGM. There are no restrictions on the participants while they wear the transmitter/sensor with regard to physical activity except for swimming. Participants will be blinded to the CGM monitor glucose levels as not to affect their activity or eating habits. The sensor will be removed by a trained study staff member by the end of day 14 of wear.

The CGM will be placed for a second time at the 8-week time interval during Liraglutide treatment and will be removed after 14 days of wear. Only obese participants will wear the CGM for a second time.

After the CGM is placed, participants will be provided with a BOOST® Original Nutritional Drink. They will be instructed to drink the BOOST on the follow day between 7:30 and 10:30am as a breakfast meal replacement (must drink on an empty stomach).

## fMRI

The original study included use of functional MRI to assess brain perfusion in the response to drinking HFCS in healthy lean and obese adolescent/young adult males and females. However, in light of the recent pandemic we would like to shift the focus of the study towards the evaluation of the effect of GLP-1 analogue on food craving and intake as well as glycemic variability and metabolic hormonal changes in response to food.

## Plasma Collection

Prior to the food snack task, a nurse will insert one IV catheter to sample blood for metabolite and hormone analysis (heated hand). Baseline measurements of leptin/ghrelin, insulin, GLP-1, cortisol and glucose will be collected. In addition, to assess how metabolic response to drinking HFCS relates to the neural responses observed, plasma samples will be obtained for leptin/ghrelin, insulin, GLP-1, glucose, and cortisol at specified interval time points. No more than 110mLs of blood will be drawn on each food snack task day.

## Eating Behavior Assessments

To assess food preference and food intake before vs. after liraglutide intervention, eating behavior will be assessed in three ways;

**Lab-based Food Brunch Task:** At baseline and during the last week of treatment, each participant will undergo the food brunch task. Participants will be given the opportunity to eat ad libitum for 30 minutes with detailed measurement of food/drink consumed and video recording to assess eating topography. We will obtain signed permission prior to any video recording and the participant will know when they are being videotaped. The videotape recording will be used for research only. The recording will not be shown to the general public and will not be identified with the subject's name, although their face may be included in the recording. Declining to be videotaped will not affect the participant's study participation or

treatment in any way.

The food brunch task is adapted from [name] on the basis of previous work on exposure to food cues and foods in the laboratory, which indicates that sufficient quantities, multiple food options and sufficient time available for eating are important variables modulating food intake. In the food brunch task, participants will be presented with a choice of the following foods, presented in 6 discrete bowls: skittles, M&Ms, chips, pretzels, cookies and popcorn. They will be offered the food and drinks and allowed to eat and drink as much as they like for 30 minutes. Video recordings will be assessed for frequency of times each bowl is touched/reached for, frequency of pick-ups and number of bites taken. The type and amount (weight and kilocalories) of food/drink consumed by each subject will be assessed before and after each session. All remaining items will be weighed by trained staff in the Yale Center for Clinical Investigation Metabolic Kitchen.

The instructions will state: "There are different foods and drinks on the tray. We will leave these here for you and you can eat and drink as much or as little as you like during the next half hour". We will draw labs at the following time intervals during the food brunch task: 0, 15 and 30 minutes.

Participants will also be asked to complete the following questionnaires during each food snack test visit at 4 time points (baseline and then q 10 minute intervals): Hunger Scale, Anxiety Scale, DES-R and Food Craving Scale.

**Real-life dietary intake:** Participants will complete a detailed 1 week food record via a smartphone app, MetricWire. This will be administered during the 14 days that the participant is wearing the CGM. For obese participants, this will be completed a total of 2 times (obese participants wear the CGM 2 times). For lean participants, this will be completed once (lean participants wear the CGM once). During these time points, a 24-hour food recall, the National Cancer Institute's (NCI) Automated Self-Administered 24-hour (ASA24®) dietary assessment tool, will also be administered and must be completed on 2 week days and 1 weekend day. Study personnel will call participants to complete the ASA24 over the phone.

Each participant will be taught how to accurately record their food and drink intake by the study registered dietician, doctors and/or nurse practitioner.

Participants will also be asked to complete the following questionnaires at the screening visit to assess food cravings and consumption and eating behaviors: Yale Food Addiction Scale (YFAS), Food Craving Inventory (FCI) and Dutch Eating Behavior Questionnaire (DEBQ). For obese participants only, these questionnaires will be repeated at the second food snack task visit.

**ASA24:** The National Cancer Institute (NCI) created the Automated Self-Administered 24-hour (ASA24®) dietary assessment tool, a web-based tool that enables multiple, automatically coded, self-administered 24-hour recalls. The ASA24 system is freely available for use by researchers, clinicians, and teachers and can be used by researchers for epidemiologic, interventional, behavioral, or clinical research. Clinicians can utilize this system to collect 24-hour recalls or food records from patients and receive complete nutrient analysis of the foods and beverages consumed during the collection timeframe. Since ASA24 was released in 2009, greater than 3,900 studies have registered to use ASA24 and over 355,000 recall or record days were collected, as of December 2017. The ASA24 system consists of a Respondent Website used to collect dietary intake data and a Researcher Website

used to manage study logistics and obtain nutrient and food group data files. Researchers do not provide the National Cancer Institute (NCI) or the ASA24 system with any identifying data for study Respondents. Rather, Researchers specify a user ID for each Respondent and download system-generated usernames and encrypted passwords that Respondents use to access the application. The ASA24 system also does not collect any identifying data directly from Respondents. However, IP address information is accessed for the purpose of routing information between the server and the Respondent's computer -- often the IP address is that of the user's Internet Service Provider (ISP). IP addresses are not stored or tracked by the ASA24 system. However, logs of connections are kept for audit trail purposes. This information is not mined in any way but would be available if there were a legal obligation to release it.

**Other:** Subjects unable to attend in person visits due to COVID-19 will be sent a weight measurement scale.

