## STATEMENT OF PURPOSE/OBJECTIVES

**Aim 1** – To investigate the effect of GLP-1 analogue (liraglutide 3.0mg) on eating behavior and food craving in individuals with obesity (age 15-39 yrs) who chronically consume SSBs ( $\geq 5$  SSBs/week).

**Exploratory Aim:** To investigate the role of specific metabolic/hormonal responses (serum leptin, insulin, glucose, GLP-1, acyl-ghrelin) induced by food consumption, and in the setting of liraglutide treatment

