## ANALYSES AND STATISTICAL CONSIDERATIONS

Analysis of subjective ratings, plasma hormonal measures, Brunch Food Task, and diet 3-day food measures will be assessed using a mixed-model repeated measures analysis (PROC MIXED SAS V9.4, Cary, NC) to assess main effects and interactions for the fixed factors of obesity status (lean vs. obese) and time (before vs. after intervention), and subjects will be the random effect factor to accommodate correlation between repeated measures. Covariate adjustment will be included for age and sex.

Using these random effects models applied to whole brain analysis for neural responses and mixed effects models for other analyses, the following specific hypotheses will be tested for each aim:

Sample size estimates are based on effect size determinations from our preliminary work and related previous research. Based on Jastreboff et al (2016) findings from lean (n=14) vs. obese (n=24) adolescents, we found an overall large effect sizes between  $d=0.65$  and  $0.56$  for the mPFC responses in the lean and obese adolescent groups, and  $d=0.68$  and  $0.53$  for the striatal (caudate) response in the lean and obese adolescents as well as an effect size  $d=0.569$  for lean vs. obese for the PFC connectivity with the striatum. The described fMRI liraglutide study by Farr et al. (n=18) found effect size placebo=0.53 and liraglutide=-0.47 for decreased activation in the parietal cortex. There are no specific studies examining the effect of liraglutide on CBF response to HFCS ingestion. Based on these earlier studies, we will include 45 subjects in our study; specifically, 15 healthy lean and 30 obese adolescents to

test the proposed hypotheses.

For the adolescents, the goal is to have pilot data inclusive of adolescents with the food snack task alone – to obtain funding inclusive of adolescent age and add to literature. The effects of the medication on eating behavior are fairly robust which is why I believe we were able to see differences in initial pilot data. The main goal is to investigate the impact on eating behavior (assessed in the food snack task) before and after the medication (so baseline vs. post intervention). The lean participants serve as “controls” in that after the medication, the individuals with obesity have eating behavior more similar to that observed in lean. We also do within subject comparison (obesity before medication vs. after) - that is the main question.

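### For GLP-1, acyl-ghrelin and leptin, the only stated post-food values follow a meal whose size the drug is expected to change, so a changed hormone response cannot be told from a smaller meal

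*Combined protocol and SAP*

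**What the plan says.** The Exploratory Aim (Statement of Purpose/Objectives) is "To investigate the role of specific metabolic/hormonal responses (serum leptin, insulin, glucose, GLP-1, acyl-ghrelin) induced by food consumption, and in the setting of liraglutide treatment". The fMRI section says the focus has moved from brain imaging to food craving and intake, glycemic variability and hormonal change in response to food.

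The food is supplied at the brunch task (Eating Behavior Assessments), at baseline and in the last week of treatment: "Participants will be given the opportunity to eat ad libitum for 30 minutes with detailed measurement of food/drink consumed". Blood sampling is set there too: "We will draw labs at the following time intervals during the food brunch task: 0, 15 and 30 minutes". The weight and kilocalories consumed are recorded for each session. Plasma Collection names the analytes for the snack-task visit but lists no times: "plasma samples will be obtained for leptin/ghrelin, insulin, GLP-1, glucose, and cortisol at specified interval time points". Its stated reason still refers to the HFCS drink and neural responses.

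The plan also contains fixed challenges:

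- **OGTT section:** a 75 g glucose drink, once in lean participants and at baseline and week 10 in obese participants. There, "blood samples will be taken for glucose and insulin assays at time points" running to 120 minutes. Acyl-ghrelin, leptin and GLP-1 are drawn fasting only.
- **CGM section:** a BOOST drink taken the morning after sensor placement. Obese participants have a second placement at week 8.

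Analyses and Statistical Considerations fits a mixed model to the plasma hormones with obesity status and time (before or after intervention) as fixed factors. It adds: "Covariate adjustment will be included for age and sex". The same section expects a strong drug effect on eating, and makes before/after eating at this task the main question.

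**The concern.** The stimulus for the hormone response is itself the main behavioral outcome. If liraglutide works as the protocol expects, the post-treatment samples at 15 and 30 minutes follow less food than the baseline samples did. A smaller change in GLP-1, ghrelin or leptin could then mean an altered response to food, the same response to less food, or both. The lean-obese contrast has the same difficulty if the two groups eat different amounts.

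The timing adds to this. The last stated draw coincides with the end of the eating window, so no stated sample shows the response after eating has finished.

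At stake is what the Exploratory Aim can conclude. A paper could report a hormonal mechanism of liraglutide when the data show only that participants ate less.

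**Working it through.** The plan states no figure on this point that could be reproduced. The sample size of 45 rests on neural effect sizes and does not bear on it. The check is to match analytes to challenges and then see what the planned model can identify.

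**1. Which analytes have a response to a fixed load?** I take the brunch task and the snack task to be the same task, and the ghrelin in Plasma Collection to be the acyl form named in the aim.

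| Analyte | Brunch (free intake) | OGTT (75 g) | BOOST under CGM |
|---|---|---|---|
| Glucose | 0, 15, 30 min | serial to 120 min | yes |
| Insulin | 0, 15, 30 min | serial to 120 min | no |
| GLP-1 | 0, 15, 30 min | fasting only | no |
| Acyl-ghrelin | 0, 15, 30 min | fasting only | no |
| Leptin | 0, 15, 30 min | fasting only | no |

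Two of the five analytes have a fixed-load response and three do not.

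**2. Draw counts.** The OGTT times are -20, 0, 10, 20, 30, 45, 60, 75, 90, 105 and 120: 11 draws, 9 after the load and 6 later than 30 minutes. The brunch has 3 draws, 2 after eating starts and none stated after the 30-minute window closes.

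**3. What the model can identify.** As a simple illustration, let the change from the pre-meal value be R = k × E, where E is kilocalories eaten and k is the response per kilocalorie. Then

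R(after)/R(before) = [k(after)/k(before)] × [E(after)/E(before)].

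The planned time effect estimates the product.

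- Unchanged k with E down 20%: 1.00 × 0.80 = 0.80.
- k down 20% with unchanged E: 0.80 × 1.00 = 0.80, the same observed result.
- k up 25% with E down 20%: 1.25 × 0.80 = 1.00, so a real change is hidden.

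Age and sex do not change between a participant's two visits in any way that carries E, so adjusting for them does not separate the factors.

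**4. How often this could mislead, under assumptions.** None of these inputs is in the documents: exact proportionality, no true change in k, 30 obese participants, a paired two-sided test at 0.05 on log R, a visit-to-visit log SD of intake change of 0.25, and a within-visit log SD of R of 0.2 to 0.4. The SD of the log difference is √(0.25² + 2 × 0.2²) = 0.377 at the low end and √(0.25² + 2 × 0.4²) = 0.618 at the high end. The noncentrality is |ln(E ratio)| × √30 / SD. The rejection rates come from 10,000 simulated trials per setting.

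| Assumed fall in intake | Noncentrality | Trials declaring a changed response |
|---|---|---|
| 0% | 0 | about 5% |
| 10% | 0.93 to 1.53 | 15 to 31% |
| 20% | 1.98 to 3.24 | 49 to 88% |
| 30% | 3.16 to 5.18 | 86 to 100% |

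Dividing by recorded kilocalories returns the rate to about 5%, but only because proportionality was built in. A fixed load needs no such assumption.

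**The case against.** The strongest reply is that the aim does not promise a response per kilocalorie. It asks about responses to food in the setting of treatment, and the response to freely chosen food is a legitimate total effect. That stands. It is why the unadjusted brunch result should be kept and labelled as including the effect of eating less. It does not support reading that result as an altered response.

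A reader might infer that the whole Exploratory Aim is confounded. The documents do not support this. Glucose and insulin are measured to 120 minutes after a fixed load, before and on treatment, and lean participants have the same baseline test. Glucose also has the BOOST challenge. The 0-minute and fasting values precede any food at that visit, so comparisons of pre-meal levels are untouched. The OGTT is only a partial substitute, though: it uses glucose rather than mixed food, it falls at week 10 rather than the last treatment week, and the analysis section does not connect it to the aim.

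A reader might also infer that sampling definitely ends at 30 minutes. The text states no later draw, but Plasma Collection leaves its times unlisted and the flow-chart cells are blank in the text available.

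Finally, the aim is exploratory, the adolescent component is described as pilot work, and kilocalories are already recorded, so an adjusted analysis could be run without redesign. That is fair, and it limits the severity. But the analysis is not planned, and intake is a post-treatment variable, so adjustment alone cannot isolate a direct hormonal effect.

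**Conclusion.** The concern holds in a limited form. For GLP-1, acyl-ghrelin and leptin, a before/after or lean-obese difference in the 15- and 30-minute brunch values cannot be separated from a difference in amount eaten under the plan as written. Glucose and insulin are less exposed, provided the plan says that the OGTT answers the question for them. Pre-meal comparisons are sound.

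The size cannot be taken from the documents, which give neither the expected fall in intake nor any hormone variance. The rejection rates above show only that the problem need not be small; they depend wholly on the assumed fall, the SDs and proportionality. The conclusion itself needs only two things: that intake differs between the visits or groups compared, and that the hormones respond to the amount eaten. The point affects the interpretation of an exploratory aim, not Aim 1 or the sample size.

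**What to change.** 1. Name the OGTT at baseline and week 10 as the before/after test of glucose and insulin response. Assay GLP-1, acyl-ghrelin and leptin at two or three of its existing draw times. Tube volumes are not stated, so first check that the added assays fit the 50 mL limit for that day.
2. Report brunch hormone change in two ways: unadjusted, described as a total effect that includes eating less; and adjusted for the kilocalories recorded at that visit, labelled as a descriptive sensitivity analysis that conditions on a post-treatment variable. Do the same for the lean-obese comparison.
3. State in the plan that brunch hormone changes will not be attributed to an altered response independent of intake.
4. List the sampling times in Plasma Collection and update its rationale, which still refers to the HFCS drink. A draw after eating ends, for example at 60 minutes, would help but is optional; check it against the 110 mL limit.

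It would be tempting to require the adjusted brunch result and the OGTT to agree before drawing a conclusion. I would not: they use different stimuli at different weeks, so disagreement would have no clear meaning.

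The cost is a few extra assays on visits already scheduled, one added covariate analysis and a few sentences of text. The adjusted estimate will be less precise. The optional draw adds one sample and about 30 minutes to the visit.

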## ASSESSING AND REPORTING ADVERSE EVENTS

### Definition

An adverse event is defined as any untoward medical occurrence in a patient or clinical investigation subject administered a pharmaceutical product and which does not necessarily have to have a causal relationship with this treatment. An adverse event can therefore be any unfavorable and unintended sign (including an abnormal laboratory finding, for example), symptom, or disease temporally associated with the use of a medicinal product or protocol-specified procedure, whether or not considered related to the medicinal product or protocol-specified procedure. Any worsening (*i.e.*, any clinically significant adverse change in frequency and/or intensity) of a preexisting condition that is temporally associated with the use of enoxaparin is also an adverse event.

Adverse events may occur during the course of the use of the IP in clinical trials or within the follow-up period specified by the protocol, or prescribed in clinical practice, from overdose (whether accidental or intentional), from abuse and from withdrawal.

**Serious adverse event.** A serious adverse event is an AE occurring during any study phase (*i.e.*, treatment, follow-up), that fulfills one or more of the following criteria:

1. Results in death
2. Is immediately life-threatening
3. Requires in-patient hospitalization or prolongation of existing hospitalization
4. Results in persistent or significant disability or incapacity
5. Results in a congenital abnormality or birth defect
6. Is an important medical event that may jeopardize the subject or may require medical intervention to prevent one of the outcomes listed above

Each AE will be graded for severity per the NCI CTCAE version 4.0, and these criteria must be used in grading the severity of AEs. The criteria can be found at:  
<http://ctep.cancer.gov/reporting/ctc.html>

For those AEs, which are not listed as part of the NCI CTCAE version 4.0, the same grading system should be used, where:

- **Mild** corresponds to an event not resulting in disability or incapacity and which resolves without intervention

- **Moderate** corresponds to an event not resulting in disability or incapacity but which requires intervention
- **Severe** corresponds to an event resulting in temporary disability or incapacity and which requires intervention
- **Life-threatening** corresponds to an event in which the patient was at risk of death at the time of the event
- **Fatal** corresponds to an event that results in the death of the patient

